4.5.2 Data Scopes

All analyses are based on two elements:

1) analysis set, which specifies which subjects will be included in an analysis; and

2) data scope, which defines the time window within which data will be included in the analysis.

This section describes the coverage of the event data scopes used for the statistical analyses. Analysis sets are described in Section 5.

The below data scopes are based on the 3 periods of the study, main treatment, extension treatment and follow up, as defined in section 4.5.1:

Data scope according to primary analysis principle (PA)

The PA data scope includes outcome events observed from the date of first administration of study intervention until the end of the main treatment period. Events occurring after the main treatment period will not be counted for primary analysis data scope.

Data scope according to total treatment analysis principle (TA)

The TA data scope includes outcome events observed from the date of first administration of study intervention until the end of the extension treatment period. Events occurring after the extension treatment period will not be counted for total treatment analysis data scope.

Data scope according to overall analysis principle (OA)

The OA data scope includes outcome events observed from the date of first administration of study intervention until the end of post-treatment follow-up period.

4.5.2.1 Exploratory data scopes

Extension period data scope (EP)

The EP data scope includes outcome events observed from the start of the extension period until the end of the extension period.

Follow up period data scope (FP)

The FP data scope includes outcome events observed from the start of the post-treatment follow-up period until the end of the post-treatment follow up period

4.6 Blind Review

There will be two data assessment lists. The first one will occur after primary completion and the second one will occur after end of study. The results of both data lists will be documented in separate lists of important deviations, validity findings and assignment to analysis set(s). Any changes to the statistical analysis prompted by the results of the review of study data will be documented in an amendment and, if applicable, in a supplement to this SAP.

The results of the final data assessment will be documented in the final list of important deviations, validity findings and assignment to analysis sets. Pharmacodynamic and pharmacokinetic values to be excluded from statistical analysis will be documented and respective flags will be incorporated in the clinical database.

4.7 Sample Size Determination

No formal statistical sample size estimates were performed.

The sample size was selected based on prior experience in ESRD with the unconjugated ASO. This study is planned to ensure the safety, tolerability, and PK/PD relationships are assessed adequately while minimizing unnecessary participant exposure. There is no plan for statistical hypothesis testing for this study. In this study, the number of subjects is considered based on the ISIS 416858-CS5 study design.

Approximately 288 participants (96 [72 active+24 placebo] per cohort) will be randomly assigned to study intervention so that an estimated 240 participants will complete the main treatment period. All participants will be randomized to 1 of 3 dose cohorts in a 1:1:1 ratio (Cohort A, Cohort B, and Cohort C). Within each dose cohort, subjects will be randomized in a 3:1 ratio to receive treatment with either Fesomersen or placebo. Considering an approximately 15% dropout rate, an estimated total of 60 participants per intervention group and the placebo group will complete the main treatment period. A participant will be evaluated once he/she was randomized and received at least one dose of study intervention. The number of evaluable and randomized participants is assumed to be similar.

Table 4-1 summarizes 95% expected range for the true population proportion of participants with a composite of MB and CRNMB bleeding. For example, with 60 participants, if 5% of them had a composite of MB and CRNMB bleeding during the main treatment period and the desired confidence level is 95%, the corresponding confidence interval would be \pm 5.51, i.e. the range of 0.0 % to 10.51%. If multiple samples were drawn from the same population and a 95% CI calculated for each sample, we would expect the true population proportion to be found within 95% of these CIs.

Sample Size	Observed Proportion *	Desired Confidence level	Corresponding two-sided confidence interval	Range for the true population proportion
60	2%	95%	±3.54	0.0% to 5.54%
	3%	95%	±4.32	0.0% to 7.32%
	4%	95%	±4.96	0.0% to 8.96%
	5%	95%	±5.51	0.0 % to 10.51%
	6%	95%	± 6.01	0.0% to 12.01%
	7%	95%	± 6.46	0.54% to 13.46%
	8%	95%	± 6.86	1.14% to 14.86%

Table 4-1: Confidence Interval for proportion of participants with a composite of MB and CRNMB Bleeding

CRNMB = clinically relevant non-major bleeding, MB = major bleeding

* The range of observed proportion is considered based on the Interim report of ISIS 416858-CS5 study where the composite of MB and CRNMB bleeding proportion for Placebo was 5.7% and for total ISIS treated= 4.5% (ISIS treated with 200mg, 250mg and 300 mg doses were 3.8%, 5.6% and 4.0% respectively)

5. Analysis Sets

5.1 Assignment of Analysis Sets

All subjects who have been randomized in the study are valid for assignment to analysis sets. The following populations are defined:

	F
Population	Description
Enrolled	All participants who sign the ICF
Full analysis set (FAS)	All participants randomized who have received at least 1 dose of study intervention. Participants will be analyzed according to the intervention they were randomized.
Safety analysis set (SAF)	All participants randomly assigned to study intervention and who took at least 1 dose of study intervention. Participants will be analyzed according to the intervention they received. If a participant was administered, in error, a different dose to that which they were randomized to, they will be analyzed according to the intervention received most frequently (i.e. at > 50% of visits), in cases where 2 different doses were administered for the same number of visits, the participant would be excluded from the safety analysis set.
Pharmacokinetic set (PK)	All Fesomersen-treated participants with at least 1 PK sample in accordance with the PK sampling schedule (Section 8.5.1 of the study protocol) and without deviation from the protocol that would interfere with the evaluation of the PK data will be included in the PK analysis.
Pharmacodynamic set (PD)	All participants with at least 1 PD sample in accordance with the PD sampling schedule and without deviation from the protocol that would interfere with the evaluation of the PD data will be included in the PD analysis.
Listing only set	All participants who signed consent but are not randomized.

Table 5-1: Populations

If the safety and full analysis sets are identical, i.e. all subjects received the treatment to which they were randomized, the full analysis set will not be used.

The planned analyses for the primary, secondary, exploratory, and PK-PD endpoints are summarized in but not limited to Table 5-2 below

Endpoints	Analysis Type	Analysis set	Data Scope
Primary Endpoint(s)	Main	SAF	PA ^{a)}
	Additional	SAF	TA ^{a)}
	Exploratory	SAF	OA ^{b)}
	Subgroup	SAF	PA ^{a)}
		SAF	TA ^{a)}
Secondary Endpoint(s)	Main	SAF	PA ^{a)}
	Additional	SAF	TA ^{a)}
	Exploratory	SAF	OA ^{b)}
Exploratory Endpoint(s)	Main	SAF	PA ^{a)}
	Additional	SAF	TA ^{a)}
	Exploratory	SAF	OA ^{b)}
		FAS	PA ^{b)}
		FAS	TA ^{b)}
	Subgroup	SAF	PA ^{a)}
	C .	SAF	TA ^{a)}
PK, PD Endpoint(s)			
Trough concentrations	Main	PK	OA
Maximum change in FXI	Main	PD	OA
antigen levels			
Maximum change in FXI activity	Main	PD	OA
levels			

Table 5-2: Sketch of the planned analyses on the endpoints

PA: Data scope according to primary analysis principle, TA: Data scope according to total treatment analysis principle, OA: Data scope according to overall analysis principle.

a) on-treatment estimand

b) treatment policy estimand

6. Statistical Methodology

The primary safety and efficacy variables will be analyzed descriptively for the following groups:

- Pooled Placebo Group (from Cohorts A, B and C),
- 40 mg Dose Group (Fesomersen from Cohort A),
- 80 mg Dose Group (Fesomersen from Cohort B), and
- 120 mg Dose Group (Fesomersen from Cohort C).

For selected analyses the pooled Fesomersen treatment arms will be presented in addition.

Incidence rates and cumulative incidences will be calculated only for endpoints with at least 1 event in a treatment arm. Hazard ratios (cause specific and sub distribution), log-rank test and Gray's test will only be calculated if there is at least 1 event in each of the compared treatment arms.

6.1 **Population Characteristics**

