9.3 Populations for Analyses

The following populations are defined:

Population	Description						
Enrolled	All participants who sign the ICF						
Full analysis set	All participants randomized who have received at least 1 dose of study intervention. Participants will be analyzed according to the intervention they were randomized.						
Safety analysis set	All participants randomly assigned to study intervention and who took at least 1 dose of study intervention. Participants will be analyzed according to the intervention they received.						
Pharmacokinetic set	All LICA-treated participants with at least 1 PK sample in accordance with the PK sampling schedule (Section 8.5) and without deviation from the protocol that would interfere with the evaluation of the PK data will be included in the PK analysis.						
Pharmacodynamic set	All participants with at least 1 PD sample in accordance with the PD sampling schedule and without deviation from the protocol that would interfere with the evaluation of the PD data will be included in the PD analysis.						
Listing only set	All participants who signed consent but are not randomized.						

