9.4.1 General considerations

9.4.1.1 Planned Methods of Analysis

Descriptive statistics will be provided by treatment group for all demographic variables, safety endpoints, and exploratory endpoints. The placebo groups from each cohort will be combined, so that there are four treatment groups to be included for analysis—40 mg, 80 mg, 120 mg, and placebo, all equal in size.

- The safety analysis set will be used for all safety endpoints, including the primary endpoint.
- The full analysis set will be used for the exploratory endpoints or otherwise specified.
- The PK analysis set will be used for the pharmacokinetic endpoints, and
- The PD analysis set will be used for the pharmacodynamics endpoints.

For categorical variables, frequencies and proportions will be provided by treatment group. For continuous variables, means, medians, standard deviations, standard error of mean, interquartile range (25th percentile, 75th percentile), and range (minimum, maximum) will be provided by treatment group. For continuous variables collected at multiple time points, the descriptive statistics will be provided at each time point.

All analyses and tabulations will be performed using SAS@ Version 9.2 or higher or if applicable, other software.

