6.4.1 Analysis of the Primary Safety Variable

The primary analysis is based on a descriptive proportion of subjects with primary endpoints (independently adjudicated) based on SAF analysis set and PA data scope. For each treatment and bleeding category, participants reporting more than one bleeding event will be counted only once using the highest severity. The frequency and percentage of participants with bleeding will be reported where the denominator will be total number of participants in each treatment group.

Estimand for the Primary Safety Endpoint:

The five attributes of the estimand are as follows:

- **Population:** The population consists of ESRD patients as described by the inclusion/exclusion criteria given in study protocol.
- Variable: The incidence of the composite of MB, CRNMB, events during the main treatment period, as assessed by the CIAC
- Treatment: Three dose groups of Fesomersen or placebo on top of standard of care
- Intercurrent events:
 - Unblinding to study intervention: the study allows unblinding of treatment assignment if the investigator deems necessary when related a bleeding or major surgery occur regardless of whether such an event occurs (treatment-policy strategy)
 - Early definitive discontinuation of study intervention or death or kidney transplant: until the occurrence of the intercurrent event (while on treatment strategy)
 - Dose reduction: regardless of whether such an event occurs (treatment-policy strategy).
- **Population-level summary:** Incidence proportion of subjects with an event by study intervention group and differences between Fesomersen treatment groups and placebo group. For the incidence proportions the exact binomial two-sided 95% confidence interval using Blaker's method will be provided. For the difference in incidence proportions the two-sided 95% confidence interval will be presented using the unstratified exact method with the standardized test statistic and inverting a two-sided test (Agresti and Min, 2000).

6.4.1.1 Additional Primary Safety Endpoint(s) Analysis:

Estimand for Time to Event Safety Endpoint:

The attributes constituting the estimand for this endpoint are the following:

- **Population:** The population consists of ESRD patients as described by the inclusion/exclusion criteria given in study protocol.
- Variable:
 - Time from first dose of intervention to MB and CRNMB events (in alignment with ISTH guidelines) up until 28 days after last study intervention

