6.4.3 Sensitivity and Supplementary Safety Analysis

To support the primary study results and to assess the robustness of the analysis, several additional sensitivity and supplementary analyses will be performed.

The primary safety endpoint will be analyzed using the same method described in Section 6.4.1.1 based on SAF analysis set and both TA and OA data scope.

In addition, analysis will be performed with additional bleeding events on SAF analysis set with PA data scope, and SAF analysis set with TA data scope:

- Minor bleeding
 - Minor bleeding will be further categorized as injection site and non-injection site bleeding events.

Additional analysis on the secondary safety endpoints will be performed based on SAF analysis set and TA data scope.

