6.4.5 Subgroup Analysis

The subgroup analyses based on baseline and demographic characteristics are planned for the treatment groups comparisons of the primary safety endpoints, the subgroups for the safety analysis are the same as those listed in section 6.2.2.3:

The analyses for the subgroups will be performed based on SAF analysis set and PA data scope and SAF analysis set and TA data scope. The results will be presented descriptively with forest plots.

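### The SAP's tie rule for mis-dosed participants removes dosed people from the safety set that carries the primary bleeding endpoint

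*SAP*

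**What the plan says.** - **Protocol 9.3** states who belongs to the safety set: "All participants randomly assigned to study intervention and who took at least 1 dose of study intervention". Grouping is as treated, and there is no exclusion for mis-dosing.
- **Protocol 9.4.1.1** adds: "The safety analysis set will be used for all safety endpoints, including the primary endpoint".
- **SAP 5.1, Table 5-1** opens with the same membership rule. Someone dosed in error is then placed with whichever intervention they got on most occasions. For ties the table states: "in cases where 2 different doses were administered for the same number of visits, the participant would be excluded from the safety analysis set". SAP Section 7 dates this text to version 2.0 and calls it a clarification.
- **SAP 6.4.1** runs the primary proportions of adjudicated bleeding on the safety set, over the PA scope. The sensitivity analyses in 6.4.3 stay on that set, over the TA and OA scopes. Section 6.4.5 keeps the subgroups there too, in the PA and TA scopes: "The analyses for the subgroups will be performed based on SAF analysis set and PA data scope".
- **SAP Table 5-2** lists five rows for the primary endpoint, all on the safety set. Full-analysis-set rows appear only under the exploratory endpoints. The table is introduced as not exhaustive.
- **Full analysis set (Table 5-1):** also requires one dose, but "Participants will be analyzed according to the intervention they were randomized", so it would keep the tied participant.

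**The concern.** Membership and grouping are separate questions. A person who received study drug belongs in the safety set, and a tie leaves only the group open. By deleting the person, the SAP departs from the protocol, from its own opening sentence, and from SAP 4.7, which says a participant is evaluated once randomised and dosed.

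The exclusion need not be neutral with respect to bleeding. The main period has six dosing visits (V5, V10, V12, V14, V16, V18), so a full-course tie needs three errors. After only two doses, a single error is a tie. Protocol 7.1.1 and 8.2.1.2 allow permanent discontinuation after a bleed. Someone mis-dosed once who bleeds and stops after two doses is excluded, while the same person continuing to a third dose of either kind has a majority dose and stays. Whether a bleed counts can then depend on whether it ended treatment.

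A remote further consequence comes from SAP Section 6, where hazard ratios, the log-rank test and Gray's test "will only be calculated if there is at least 1 event in each of the compared treatment arms". If the lost bleed were a group's only one, those comparisons would not be produced.

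**Working it through.** **Text check.**

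| Question | Protocol 9.3 | SAP Table 5-1, opening sentence | SAP Table 5-1, tie clause |
|---|---|---|---|
| Is a randomised participant with at least one dose in the set? | Yes | Yes | No, if dosed in error with two doses at equally many visits |
| Which group? | As received (silent on ties) | As received; majority dose if mis-dosed | None |

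The clause covers dosing errors only. A step-down of Cohort C recommended by the DMC is not an error and does not trigger it.

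**Inputs for size.** SAP 4.7 gives 72 active plus 24 placebo per cohort, so 72 in each dose group and 3 × 24 = 72 in pooled placebo. Its table footnote gives earlier-study bleeding proportions of 5.7% (placebo) and 4.5% (all active). The number of tied participants is not given; one is assumed.

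**The plan's own precision figure.** 1.96 × √(0.05 × 0.95 / 60) = 5.51 points, matching Table 4-1. That table is not in dispute.

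**Effect of one exclusion.** With x bleeders among n, losing a bleeder gives (x − 1)/(n − 1) and losing a non-bleeder gives x/(n − 1). Intervals are Blaker 95%, the SAP's method.

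| Case | All dosed kept | One excluded | Shift (points) |
|---|---|---|---|
| Bleeder lost, 4 events | 4/72 = 5.56% (1.92–13.43) | 3/71 = 4.23% (1.16–11.51) | −1.33 |
| Bleeder lost, 1 event | 1/72 = 1.39% (0.07–7.14) | 0/71 = 0% (0–5.02) | −1.39 |
| Non-bleeder lost, 4 events | 4/72 = 5.56% (1.92–13.43) | 4/71 = 5.63% (1.95–13.62) | +0.08 |
| Bleeder lost, three active groups pooled | 10/216 = 4.63% (2.4–8.2) | 9/215 = 4.19% (2.1–7.7) | −0.44 |

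The pooled row uses 216 × 0.045 = 9.7, rounded to 10 events. For scale, the placebo–active gap in the earlier study was 5.7 − 4.5 = 1.2 points.

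**How often a group has exactly one event.** 72 × 0.045 × 0.955^71 = 12.3%; 72 × 0.057 × 0.943^71 = 6.4%. Both are before allowing for the rarity of that one bleeder also being a tied participant.

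**The case against.** The strongest reply has four parts.

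1. The missing full-analysis-set version is not itself a fault, because the protocol assigns the safety set to the primary endpoint and the SAP complies. Table 5-2 is not exhaustive and SAP 6.4.3.1 names no set, so such an analysis is unlisted but not ruled out. This stands. The gap matters only because it means nothing listed recovers the participant.
2. As-received grouping cannot settle a tie, and the randomised group credits half the doses to a level not given at those visits. If the tie went to the other dose, the first group would show 3/71 even with the participant kept, and the bleed would move to the other group. This stands as a limit on the illustration: the group is a judgement. It does not justify counting the bleed in no group, and the majority rule already attributes mixed exposure to one group.
3. The exclusion would not be hidden. SAP 4.6 requires lists of analysis-set assignments, bleeds are still reported and adjudicated, and the DMC sees unblinded data. This is true, but none of it restores the case to the primary table.
4. Injections are given on site with vial and identity checks (Protocol 6.4), so ties may never occur. The suppressed hazard-ratio comparisons are exploratory and the protocol plans no hypothesis testing. Both points stand and keep the severity low.

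**Conclusion.** The concern holds and is minor. The tie clause is wrong as written: it removes a dosed, randomised participant from a set that both documents define as all dosed participants, and it does so for the primary endpoint. The practical effect may be nil. It requires a dosing error and an exact tie, and is material only if that participant bled. Given one such case in a group of 72, the proportion falls by about 1.3 to 1.4 points (assuming one or four events and that the participant would have counted in that group), with widely overlapping intervals. Losing a non-bleeder changes almost nothing.

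**What to change.** 1. Delete the exclusion clause and keep every randomised participant with at least one dose in the safety set.
2. Assign ties by one stated rule, for example the randomised group. The same rule should cover three or more doses with none above half of visits, which the SAP also leaves open.
3. List mis-dosed participants with the doses received and their adjudicated bleeds.
4. SAP 6.5 shows that the primary analysis is complete, so first check the analysis-set assignment lists for anyone excluded under the clause. If there was nobody, one sentence in the report closes the matter. If there was someone, document the change by amendment as SAP 4.6 provides, show corrected beside original results as a disclosed post-unblinding change, and give the alternative tie assignment as a sensitivity analysis.

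The cost is a short amendment, one derivation and one listing. The affected tables are rerun only if someone was excluded, and no new data are needed. The downside is that a participant with mixed exposure is attributed to a single dose group.

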6.2 Efficacy

6.2.1 Analysis of Exploratory Efficacy Variable(s)

Two exploratory efficacy variables will be considered.

First exploratory efficacy composite endpoint consisting of the following components:

• Death due to MI, ischemic stroke, pulmonary embolism (PE), non-CNS systemic embolism (SE) and undetermined - presumed cardiovascular death

- Stroke (ischemic or undetermined type)
- MI
- Major amputation of vascular etiology
- Acute limb ischemia
- Symptomatic VTE
- Systemic embolism

Second exploratory efficacy endpoint:

• Thrombosis of the arterio-venous grafts or fistulas

The frequency and percentage of participants with an exploratory efficacy event will be reported where the denominator will be total number of participants in each treatment group, within the SAF analysis set and PA data scope. The corresponding exact binomial two-sided 95% confidence interval calculated using Blaker's method will be provided.

Exposure adjusted incidence rate (100 person-years) analysis will be performed by treatment group and overall. In addition, the analysis of the exploratory efficacy variable will be conducted as a descriptive time to first event analysis separately for the three Fesomersen dose groups and placebo, similar to the primary safety analysis (i.e. only treatment emergent efficacy events which occurred during the main treatment period will be considered). Thus, the descriptive analysis focuses on estimating the efficacy under constant BAY2976217 concentration during chronic treatment. This analysis will be based on SAF analysis set and the PA data scope.

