- Treatment: Three dose groups of Fesomersen or placebo on top of standard of care
- Intercurrent events: Of interest is the response to treatment while the participant is
 - o alive (intercurrent event "death") and
 - exposed to study intervention (intercurrent event "premature discontinuation of treatment"),

i.e., both intercurrent events are handled using the same strategy "while alive" or "while on treatment".

Population-level summary:

Death and premature end of exposure to assigned treatment (last administration of assigned treatment plus 28 days) considered a competing event for the safety analysis.

The cumulative incidence function for the event-of-interest as well as the associated competing event(s) together with the corresponding confidence interval will be estimated for each treatment arm using Aalen-Johansen estimators.

The cumulative incidence, i.e. the probability of having a specific event, E, at or before a timepoint, t, $P(T \le t, E = 1)$, will be estimated for time-to-event endpoints by Aalen-Johansen estimators with the competing event.

The difference of the Aalen-Johansen estimators between 40mg Fesomersen and placebo and 80mg Fesomersen and placebo and 120mg Fesomersen and placebo will be presented with a 90% confidence interval.

As the Aalen-Johansen estimator is approximately normal distributed (Aalen, Borgan and Gjessing 2008), the difference of Aalen-Johansen estimators is approximately normal distributed. Thus, the two-sided 90% confidence interval is obtained via:

$$\left[(\widehat{A}J^{TRT}(day) - \widehat{A}J^{Control}(day)) \pm z_{0.95} \sqrt{\sigma^2(\widehat{A}J^{TRT}(day)) + \sigma^2(\widehat{A}J^{Control}(day))} \right]$$

with $\widehat{AJ}^{TRT}(day)$ the Aalen-Johansen estimator for Fesomersen (TRT) at study day, $z_{0.95}$ the 95% quantile of the standard normal distribution and $\sigma^2(\widehat{AJ}^{TRT}(day))$ and $\sigma^2(\widehat{AJ}^{Control}(day))$ are the estimated variances of the Aalen-Johansen estimators at study day, estimated with the Aalen method.

Rates

Cause-specific incidence rates will be calculated for each treatment arm with an 90% confidence interval.

The on-treatment incidence rate will be expressed a "subjects with an event – per 100 participant years". For that the following formula is used:

$$IR_{adj} = \frac{\#Participants with an event}{\sum time under treatment (in days)/(100 * 365.25)}$$

The 90% confidence interval for the exposure-adjusted IR will be computed as

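### SAP Table 5-2 labels the exploratory follow-up (OA) bleeding analysis as treatment policy, but 6.4.3 runs it with a while-on-treatment method; two FXI rows and two FAS rows also need aligning

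*SAP*

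**What the plan says.** **Bleeding.** Table 5-2 (SAP 5.1) pairs each endpoint with an analysis set, a data scope and an estimand footnote. For the primary endpoint in the safety set (SAF), the main-period scope (PA) and total-treatment scope (TA) are marked on-treatment. The exploratory OA row is marked "b) treatment policy estimand".

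- SAP 4.5.2 describes the second element of every analysis as the "data scope, which defines the time window within which data will be included in the analysis". For OA: "The OA data scope includes outcome events observed from the date of first administration of study intervention until the end of post-treatment follow-up period".
- SAP 6.4.3 analyses the primary safety endpoint "using the same method described in Section 6.4.1.1 based on SAF analysis set and both TA and OA data scope".
- SAP 6.4.1.1 defines the variable as "Time from first dose of intervention to MB and CRNMB events (in alignment with ISTH guidelines) up until 28 days after last study intervention". It applies a while-alive or while-on-treatment strategy to death and premature discontinuation, and states: "Death and premature end of exposure to assigned treatment (last administration of assigned treatment plus 28 days) considered a competing event for the safety analysis". Its incidence rate divides by "time under treatment (in days)/(100 * 365.25".

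**Exploratory efficacy.** In the time-to-event part of SAP 6.2.1, "only treatment emergent efficacy events which occurred during the main treatment period will be considered". SAP 6.2.2 applies the 6.2.1 method under TA and OA as well.

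**FXI.** Table 5-2 assigns OA to maximum change in FXI antigen and activity. SAP Table 2-1, SAP 6.3.2.1 and protocol 9.4.5 restrict both to the main treatment period.

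**FAS rows.** The exploratory FAS/PA and FAS/TA rows carry the treatment-policy footnote; the SAF rows with the same scopes carry the on-treatment one. SAP 5.1 drops the FAS if it is identical to the SAF.

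**The concern.** What separates footnotes a and b is how discontinuation of study drug is handled. A treatment-policy analysis counts bleeding whether or not the participant has stopped; the method assigned to the OA row ends at, or competes out, exactly that intercurrent event. Unblinding and dose reduction do not explain the difference, because the on-treatment primary estimand in 6.4.1 already handles both by treatment policy.

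The data for a treatment-policy estimate are collected. Early stoppers enter the 16-week follow-up (protocol 7.1.1), bleeding is evaluated to the end of follow-up (8.2.1), and bleeds go to the adjudication committee (8.3.10). Protocol 2.3 justifies the long observation by the drug's prolonged pharmacodynamic effect. At stake is the adjudicated MB/CRNMB estimate over follow-up. From the same text, one programmer could repeat the on-treatment result and another could produce follow-up bleeding for completers only, both under a treatment-policy label.

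For FXI, a maximum taken over more samples can only stay the same or grow. The same secondary endpoint could therefore differ between the primary snapshot and the final analysis.

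**Working it through.** **Window check.** Protocol 7.1.1 gives 20 weeks from last dose: 4 on-treatment + 16 follow-up = 20, which reproduces. The 6.4.1.1 variable stops at 4 of these 20 weeks.

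**Inputs.** 72 per group (protocol 9.2: three active groups of 72; pooled placebo 3 × 24 = 72). Dropout about 15%: 0.15 × 72 = 10.8, taken as 11. Follow-up 16 weeks = 112 days.

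**Reading A: OA replaces both the event window and the time at risk.** This is the natural reading of 4.5.2. Premature end of exposure remains a competing event, so early stoppers leave the risk set at last dose + 28 days.
- Follow-up available per arm: 72 × 112 / 365.25 = 22.1 person-years.
- Follow-up removed: 11 × 112 / 365.25 = 3.4 person-years; 11/72 = 15%.
- With the plan's 60 completers per group, 12 stop: 12 × 112 / 365.25 = 3.7 person-years; 12/72 = 17%.
- The loss is smaller if some early stoppers also leave the study. It is larger if others stop prematurely during the extension, for which the documents give no rate.

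**Reading B: 6.4.1.1 applied literally.** No follow-up bleeding counts for anyone.
- Follow-up unused: 61 × 112 / 365.25 = 18.7 person-years (only completers followed) to 22.1 (all followed).
- On-treatment time, with early stoppers' last dose spread evenly over doses 1 to 5 (mean 84 days on treatment): (61 × 168 + 11 × 84) / 365.25 = 30.6 without extension; (61 × 336 + 11 × 84) / 365.25 = 58.6 with full extension.
- Unused share of OA person-time: 18.7 / (18.7 + 58.6) = 24% to 22.1 / (22.1 + 30.6) = 42%.

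**Illustrative event counts.** Assume the CS5 interim proportions (4.5% to 5.7%) apply to 24 weeks and the hazard is unchanged off drug. First events in follow-up = n × (1 − p) × [1 − (1 − p)^(112/168)]. The bracket is 0.0302 for p = 0.045 and 0.0384 for p = 0.057.
- Reading A, n = 11: 11 × 0.955 × 0.0302 = 0.3 to 11 × 0.943 × 0.0384 = 0.4 participants per arm.
- Reading B: 61 × 0.955 × 0.0302 = 1.8 to 72 × 0.943 × 0.0384 = 2.6 participants per arm.
- Main period for comparison: 72 × 0.045 = 3.2 to 72 × 0.057 = 4.1.

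These counts are soft. CS5 treatment lasted 26 weeks, and the formula conditions on one 24-week event-free period, so it does not fit the full-extension case.

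**FXI samples after first dose (protocol Table 8-1).** Main period: V5 2, V6–V9 4, V10 3, V11–V14 4, V16 1, V18–V22 5 = 19. Under OA: 19 + 2 (FU1, FU4) = 21 without extension, and 21 + 6 (V23–V28) = 27 with full extension. The effect on the maximum itself cannot be derived from the documents.

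**Why PA is not the right replacement for FXI.** For participants who do not enter the extension, PA ends at last dose + 28 days (SAP 4.5.1). Visit 22 is Day 169 and the Visit 18 dose is Day 141: 169 − 141 = 28 days, with a +5-day window. After an on-time Visit 18 dose, a Visit 22 sample drawn 29 to 33 days later would fall outside PA.

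**FAS rows.** PA ends at last dose + 28 days, or at the Visit 22 dose for extension entrants. TA ends no later than last dose + 28 days. Moving from SAF to FAS changes the grouping and the mis-dosing rule, not the handling of discontinuation, so one window carries two labels.

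**The case against.** The best defence is that Table 5-2 calls itself a sketch, that 5.1 says the analyses are not limited to it, and that the OA definition has no discontinuation cut-off. A crude proportion of SAF participants with an adjudicated MB/CRNMB under OA, in the manner of 6.4.1, would then be a treatment-policy summary within the available follow-up. This is right as far as it goes. A reader might infer that no reading of the SAP yields the labelled estimand, and the documents do not support that. But the current 6.4.3 names only 6.4.1.1. The SAP history entry about replacing repeated text with a reference to 6.4.1 hints at a wider intent without changing the instruction.

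Second, 4.5.2 makes the data scope set the window, so the literal reading is not the natural one. This also stands, and it is why 15% of follow-up person-time, not 24% to 42% of OA person-time, is the headline figure. A reader might also infer a rate with OA events over on-treatment time. That needs someone to mix OA events with a formula introduced as an on-treatment rate; the SAP does not ask for it.

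Third, SAP 4.5.2.1 defines a follow-up-period scope, 6.4 promises analyses by period, and the overall TEAE tables run through follow-up. These are partial safeguards: no section assigns the follow-up scope to adjudicated bleeding.

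Fourth, the FXI text already states the right window, and the treatment-policy label on the FAS rows is partly defensible because grouping is as randomized. Both points reduce these items to table corrections.

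**Conclusion.** The mismatch is real and limited. As written, 6.4.3 does not deliver the treatment-policy analysis that Table 5-2 lists for bleeding under OA. On the natural reading it loses early stoppers' follow-up: up to about 3.4 of 22.1 person-years per arm (15%), given 72 per arm, 11 early stoppers and full follow-up of all. Under the stated hazard assumption that is well under one participant per arm. On the literal reading it adds no follow-up bleeding at all.

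A reader might take this as a flaw in the primary result. It is not: the SAF/PA analysis is labelled and specified consistently, the OA row is exploratory, and the sample-size section plans no hypothesis test. The TA bleeding analysis also matches its on-treatment label. Exploratory efficacy under TA and OA needs a matching clarification, because the main-period restriction in 6.2.1 is carried over by reference. The FXI rows are a table-versus-text conflict of unknown numerical effect. The FAS labels matter only if FAS and SAF differ.

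**What to change.** 1. **SAP 6.4.3.** State that for OA the event window and person-time run from first dose to the end of available follow-up, that only death is a competing event, and that end of exposure is not. Add the crude OA proportion as in 6.4.1.
2. **SAP 6.2.2.** State that the main-period restriction in 6.2.1 does not apply when the method is used under TA or OA.
3. **Table 5-2, FXI rows.** Replace OA in both maximum-change rows with the main treatment period, samples through Visit 22 including its visit window. Do not use PA, which could exclude Visit 22 samples of participants who do not enter the extension.
4. **Table 5-2, FAS rows.** Minor, and only if FAS differs from SAF: relabel FAS/PA and FAS/TA as on-treatment (as randomized). Leave PA and TA themselves as defined, because the primary SAF analyses use them.
5. **SAP history.** Record that these changes came after the unblinded primary analysis (SAP 6.5 places that analysis before the current version) and that they affect only supplementary or exploratory bleeding and efficacy outputs and the FXI table rows.

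The cost is two table cells, two labels, a short method paragraph and one sentence, plus reprogramming of the affected outputs. No new data are needed.
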